Alternative Hypothesis (H1):

There is a significant difference in the reduction of Demodex mite count among patients with Demodex Blepharitis treated with at least one of the following therapies: Low Level Light Therapy (LLLT), Intense Pulse Light Therapy (IPL), Combined LLLT + IPL, greater than Mechanical with pharmacological Treatment.

[figure not shown]
Hypotheses

- LLLT or IPL, will be equally effective in reducing Demodex mite count and improving ocular surface parameters.
- IPL + LLLT will be more effective than LLLT or IPL alone in reducing Demodex mite count and improving ocular surface parameters.

7. Keywords

Demodex blepharitis, MGD, LLLT, IPL, Demodex mite count, Demodex mite eradication, Ocular surface parameters

Conceptual framework

Variables

Independent variables:

the different treatment modalities:

- 1.Low Level Light Therapy (LLLT)
- 2.Intense Pulse Light Therapy (IPL)
- 3.Combined LLLT + IPL
- 4.Mechanical with pharmacological treatment

Dependent variables: Mean Demodex Count, MGD Staging, OSDI Questionnaire, Meibum Quality, Meibum Expressibility, Telangiectasia Grading (0-3), Surface Staining (NEI Grading System), % Meibomian Gland Loss (MGL), Lipid Layer Thickness, Noninvasive Break-Up Time (NIBUT), Tear Meniscus Height (TMH),

8. Research Design

Single Center, 2x2 Factorial Randomized Control Trials

9. Research Methodology

Target Population: Demodex blepharitis patients at the Department of Ophthalmology, King Chulalongkorn Memorial Hospital.

This is a single-center, prospective, 2x2 factorial Randomized Control Trials involving outpatients with Demodex blepharitis presenting at the Department of Ophthalmology, King Chulalongkorn Memorial Hospital (KCMH) from Nov 2024 to Nov 2025.

The approach to participants: involves patients under the care of the research physician. They are recruited through advertisements and contacted through the patient's physician to introduce the researcher and seek volunteer participation.

The inclusion criteria consist of:

1. All patients who received a definite diagnosis of demodex blepharitis based on cylindrical dandruff at the base of the lashes and the presence of at least one alive demodex mites on eyelid margin by microscopy
2. Age >18 years.
3. Patients who can understand and follow the study instructions and can adhere to the scheduled follow-up plan.

The exclusion criteria consist of:

1. Patients who received previous treatment IPL or LLLT

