LLLT : The blue MY MASK-E (Espansione Marketing S.p.A., Bologna, Italy) (Thai FDA No 66-2-2-0012685)

- No eye shields
- Applying a special mask for 15 minutes, once a week for 4 weeks

ShamLLT : the MY MASK-E (Espansione Marketing S.p.A., Bologna, Italy) – No eye shields, applying a power off special mask for 15 minutes , once a week for 4 weeks

ShamIPL : the Eye-light device (Espansione Marketing S.p.A., Bologna, Italy) - Protective eye shields, 5 time for each eye with flashes of light off.

Epilation Strategies

the Modified Coston method as outlined by Gao et al. in 2005. In this method, two lashes containing cylindrical dandruff (CD) then additional **rotated around itself** were extracted from each eyelid of every participant using fine forceps. These lashes were then individually placed at opposite ends of a glass slide for observation under a slit-lamp biomicroscope (SL220; Carl Zeiss, Oberkochen, Germany) at a magnification of $\times 25$. This process resulted in four lashes of right eye being prepared across two slides for each participant. A coverslip was applied to each lash, followed by the slow pipetting of 20 μL of saline at the coverslip's edge until it surrounded the lash. Subsequently, 20 μL of 100% alcohol was pipetted at the same edge, extending the counting period for up to 20 minutes to facilitate the migration of embedded Demodex from the CD. The Demodex count was performed thrice under the microscope, and all samples were photographed using standard procedures by the same specialist. The presence of Demodex in at least one of the eight eyelashes was considered Demodex-positive

10. Data Collection:

Primary Outcome:

Mean of Demodex Count - the number of Demodex mites per eyelash on a total of 4 collarettes lashes epilation (2 from upper eyelid ,2 from lower eyelid and identification by anatomical imaginary line of nasal and temporal limbus) per right eye in 30 days after end of treatment. (8th week)

Secondary Outcomes:

1.Mean of Demodex Count - per right eye in 90 days after end of treatment.(16th week)

2.MGD staging (Severity)

[figure not shown]
OSDI questionnaire used to evaluate ocular dry eye symptoms.

OCULAR SURFACE DISEASE INDEX®					
Please answer the following questions by checking the box that best represents your answer.					
Have you experienced any of the following during the last week:					

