2nd-5th visit	
 - 1st – 4th week : Treatment session 1 per week x 4 weeks - 8th week : 1 month after treatment (2nd Data correction+Epilation)
6th visit	- 16 th week : 3 months after treatment(3 rd Data correction+Epilation)

All data will be collected using Microsoft Excel version 16.65 (Microsoft Inc, USA) and analyzed using SPSS Statistics.

Informed consent process: The study includes an informed consent (Board consent) process that allows the use of research data for future studies without the need for additional consent. . Data will be collected after this process and recorded by the investigator in a manner that subjects cannot be identified

Log book:

Provide a paper logbook to all participants to record compliance and prevent any potential co-intervention by patients or caregivers.

11. Data Analysis and Statistics

Sampling technique and Sample size: N=22 in each arm by

1-Way ANOVA Pairwise, 2-Sided Equality

$$n = 2\left(\sigma \frac{z_{1-\frac{\alpha}{2\tau}} + z_{1-\beta}}{\mu_A - \mu_B}\right)^2$$

$$1 - \beta = \Phi(z - z_{1-\alpha/(2\tau)})_+ \Phi(-z - z_{1-\alpha/(2\tau)}), z = \frac{\mu_A - \mu_B}{\sigma \sqrt{\frac{2}{n}}}$$

$$n = 2 \left(3.56 \frac{z_{1-\frac{0.05}{2\tau}} + z_{1-\beta}}{3.18 - 1.59} \right)^2$$

$$1 - \beta = \Phi(z - z_{1-\alpha/(2\tau)})_+ \Phi(-z - z_{1-\alpha/(2\tau)}), z = \frac{3.18 - 1.59}{3.56 \sqrt{\frac{2}{n}}}$$

n = Sample size (per pair) = 36, Each arm = 18, 20% drop out = 21.6 = 22 per arm

Φ = the standard Normal distribution function

Φ^{-1} = the standard Normal quantile function

α = Type I error, Significance level = 5%

β = Type II error, Power (1 - β): 80%

τ = the number of comparisons to be made = 6

Relative difference (δ) = 50% (or 0.50) by our expert opinion of minimal clinical significant difference

From previous study(28)

Standard deviation (σ) = Assume an estimated value based on available data or literature (28) = 3.56

(SD Demodex count at baseline)

$\mu_A = 3.18$

$\mu_B = 1.59$

Statistical analysis, plan, and data management

Demographic and baseline clinical characteristics will be presented as percentages for categorical data and as mean with standard deviation or median with interquartile range (IQR) for continuous data.

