For outcome ,Continuous data : Meibomian gland area ratio, Meibomian gland length and width,Meibomian gland diameter deformation index ,Meibomian gland tortuosity index, Meibomian gland signal index should be analyzed using ANOVA, while binary outcomes and ordinal data Meibomian gland dysfunction staging (severity) should be assessed using the chi-square test.

Any unavailable data will be treated as missing and will not be included in any calculations. The report will specify the percentage of missing data in each category. Statistical significance will be determined by a p-value < 0.05.

12.Ethical Consideration

The submission of the research proposal to the Institutional Review Board on Human Research at the Faculty of Medicine, Chulalongkorn University marks a pivotal step in ensuring the ethical oversight and approval of the prospective Randomized Control Trial (RCT)

Respect for Person:

Informed Consent: The principle of respect for persons underscores the importance of obtaining informed consent. Ensuring that participants have a clear understanding of the study's purpose, procedures, potential risks, and benefits is crucial.

Researchers employ transparent and comprehensive communication in the informed consent process, elucidating the randomization process, details of each intervention, and the freedom to withdraw at any point without repercussions.

Researchers will provide comprehensive information to ensure that volunteers understand the research well and make independent decisions regarding participation, without coercion or undue influence. If volunteers have legal representatives or proxies, they will be the ones reviewing the informed consent document and providing witness signatures. Researchers will seek permission from the hospital director at Chulalongkorn Hospital and will anonymize data using codes without disclosing patients' names, surnames, or hospital identification numbers.

Beneficence/Non-maleficence:

Risk-Benefit Assessment: Ethical research necessitates a careful evaluation of potential benefits against risks. Researchers must strive to maximize the positive outcomes of the study while minimizing any harm to participants.

Continuous monitoring of the interventions for unexpected risks and a commitment to modify or halt the trial if harms outweigh benefits are imperative to uphold the principles of beneficence and non-maleficence.

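### The sample-size formula with the plan's own inputs gives 122 per arm, not 18; at 18 per arm, pairwise power is about 10% (τ = 6) or 27% (unadjusted), not 80%

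*Combined protocol and SAP*

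**What the plan says.** Section 11 (Data Analysis and Statistics) sizes the trial for two-sided pairwise comparisons within a one-way ANOVA. It prints a formula for n, a power expression, and both again with σ and the means filled in. The inputs are:

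- a 5% significance level;
- power: "β = Type II error, Power (1 - β): 80" per cent;
- comparisons: "τ = the number of comparisons to be made = 6";
- means of 3.18 and 1.59, a 50% relative difference described as the minimal clinically significant one;
- spread: "Standard deviation (σ) = Assume an estimated value based on available data or literature (28) = 3.56", glossed as "SD Demodex count at baseline".

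The result is "n = Sample size (per pair) = 36, Each arm = 18, 20% drop out = 21.6 = 22 per arm".

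Three other statements bear on how that result is read. Section 10 sets the primary outcome as the mite count "per right eye in 30 days after end of treatment. (8th week". The analysis paragraph of Section 11 says "Statistical significance will be determined by a p-value < 0.05" and does not mention the six comparisons. Section 6 hypothesises that "LLLT or IPL, will be equally effective in reducing Demodex mite count and improving ocular surface parameters".

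**The concern.** The difference to be detected is 1.59 and the SD is 3.56, a standardised difference of 1.59/3.56 = 0.45. A difference of that size, tested two-sided with a six-fold Bonferroni adjustment, cannot be detected with 80% power in 18 per arm. The stated figure therefore does not look like the output of the formula printed just above it.

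This calculation is the only justification given for 22 per arm, and it concerns the primary outcome. If the true power is far below 80%, non-significant pairwise results are the likely outcome even when the clinically important difference exists. Because Section 6 expects LLLT and IPL to be equally effective, such a result could be misread as confirming that hypothesis.

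**Working it through.** **Inputs (all from Section 11).** σ = 3.56; difference = 3.18 − 1.59 = 1.59; α = 0.05 two-sided; τ = 6; power 80%. Hence z(1 − 0.05/12) = 2.638 and z(0.80) = 0.842, with sum 3.480. Unadjusted, z(0.975) = 1.960.

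**1. The plan's formula.** n = 2[σ(z₁₋α/₂τ + z₁₋β)/(μA − μB)]²

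- τ = 6: n = 2(3.56 × 3.480/1.59)² = 121.4, so 122.
- Unadjusted: n = 78.7, so 79.

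The stated 36 is not reproduced.

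**2. What n counts.** The plan defines z = (μA − μB)/(σ√(2/n)). The quantity σ√(2/n) is the standard error of a difference between two groups of n each, so n is per arm. For a pairwise test there is nothing to halve.

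**3. Power at the planned size.** The plan's expression is Φ(z − c) + Φ(−z − c), with c = 2.638 or 1.960. At n = 18, z = 1.59/(3.56√(2/18)) = 1.340, so at τ = 6 the power is Φ(−1.298) + Φ(−3.978) = 0.097.

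| Evaluable per arm | τ = 6 | Unadjusted |
|---|---|---|
| 18 | 9.7% | 26.8% |
| 22 (no dropout) | 12.4% | 31.6% |
| 36 | 22.9% | 47.4% |

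At 18 per arm the noncentral t gives slightly less: 8.6–9.1% and 25.6–26.2%, depending on the error degrees of freedom.

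**4. What 18 per arm could support.** For 80% power the difference would have to be 4.13 (τ = 6) or 3.32 (unadjusted). Both exceed the plan's higher mean of 3.18, so neither is possible as a reduction from that mean. Alternatively, with the difference kept at 1.59, the SD would have to be 1.37 or 1.70.

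**5. Attempts to recover 18 or 36 with SD 3.56.**

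- One-sided test: 105 per arm (τ = 6) or 62 (unadjusted).
- Formula's n read as a pair total: about 61 per arm (τ = 6) or 40 (unadjusted).
- Overall F test: 56 to 111 per arm, depending on the pattern of means.
- Pooled factorial margins, 36 v 36, unadjusted: 47.4% power, with a detectable difference of 2.35.

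None reproduces the stated result.

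**6. If 3.56 were a variance (SD = √3.56 = 1.887).** The formula gives 34.1, so 35 per arm. A two-group t calculation gives 78.7% power at 35 and 80.2% at 36. This may be where 36 came from, but the documents do not say. That 36 would still be per arm. Power at 18 per arm would be 45.6% (τ = 6) or 71.5% (unadjusted).

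**7. Precision.** With SD 3.56 and 18 per arm, the 95% confidence interval for a pairwise difference is ± 2.032 × 3.56 × √(2/18) = ± 2.41, wider than the 1.59 the plan calls clinically important.

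**8. Dropout.** 22 × 0.8 = 17.6 evaluable, slightly under 18. The plan multiplies by 1.2 (18 × 1.2 = 21.6); retaining 18 after 20% loss needs 18/0.8 = 22.5, so 23. This is minor beside the main error.

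**The case against.** The strongest objection is that the trial is a 2×2 factorial. If 36 were the number per factorial margin, 18 per arm would be the right halving. That is true of a main-effects analysis, so the criticism of the halving applies to pairwise tests. But Section 11 names a pairwise test, and τ = 6 is the number of pairs among four arms. With SD 3.56 a 36 v 36 main effect has only 47.4% power at unadjusted 5%. Only if 3.56 is a variance does it do well (94.7%), and that is not the calculation presented.

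The variance reading can also be challenged as back-fitting. Section 11 calls 3.56 a standard deviation twice and uses it as σ. The match to 36 also depends on two-group degrees of freedom: with the pooled error of a four-arm ANOVA, 35 already reaches 80.0%. This stands. The reading is a possibility to check, not a finding, and the conclusion does not rely on it.

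Finally, the multiplicity and equal-efficacy points go beyond the arithmetic. A 0.05 threshold is compatible with adjusted p-values, and the plan nowhere says that non-significance will be taken as equivalence. That is fair. Both points are secondary: they affect which power figure applies and how a null result is read. None of these objections restores 18 per arm with 80% power.

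**Conclusion.** The concern holds. On the printed inputs the plan needs 122 evaluable per arm for its pairwise comparisons, about 6.8 times the 18 stated (122/18). Power at 18 per arm is 9.7% at τ = 6 or 26.8% unadjusted, against 80% claimed. Even if 3.56 is a variance, 18 per arm falls short for the stated pairwise test, at 45.6% or 71.5%.

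The failure to reproduce 36 is plain arithmetic. The power figures also assume a normal approximation, a common SD, and a week-8 SD equal to the baseline SD. The plan gives no week-8 SD, and no correlation or covariate adjustment that would reduce n, so achieved power could differ if the post-treatment spread differs.

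**What to change.** 1. Check in cited source 28 whether 3.56 is an SD or a variance, and state which.
2. Treat the formula's n as per arm; delete the per-pair label and the halving.
3. Withdraw the 80% claim. If 3.56 is an SD, the replacement could read: *With SD 3.56 (baseline count), a difference of 1.59, two-sided α = 0.05 and τ = 6, 122 evaluable participants per arm are required for 80% power. The trial randomises 22 per arm; with 20% dropout about 18 (17.6) are evaluable. At 18 per arm, power per pairwise comparison is about 10% at α/6 and 27% at unadjusted 0.05. The differences detectable with 80% power are 4.13 and 3.32, both above the assumed mean of 3.18. These figures assume that the week-8 SD equals the baseline SD.* If 3.56 is a variance, state 35 per arm by the plan's formula (36 by a two-group t calculation), with 46% or 72% power at 18.
4. State which multiplicity rule the primary analysis will use, so that one power figure applies.
5. As a secondary step, report 95% confidence intervals for the differences and say that non-significance will not be read as equal efficacy.

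The cost is protocol and SAP wording, one source check, and a less favourable power statement. No extra participants are needed for this correction, because it discloses the power and does not try to restore it. Restoring 80% on the printed inputs would take 122/0.8 = 152.5, so 153 randomised per arm. A change of primary comparison is optional and not part of this point.

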2. Poor compliance with eyelid scrubbing using tea tree oil (TTO)
3. Dead demodex mite on lash.
4. Contraindication of IPL: Skin Fitzpatrick scale V/VI, patients with pigmented lesions on the treatment area (Eyelid, Cheek).
5. Pregnancy or breastfeeding.
6. Active Skin disease: facial skin cancer, graft-versus-host disease, systemic lupus erythaematosus
7. Active eye infection: recurrent herpes simplex
8. Other lid disease ocular trauma, ocular deformity scar, exophthalmos, eyelid insufficiency
9. Patients with pigmented lesion on area of treatment.

We will use computer-generated random number allocation into 4 groups in a 1:1:1:1 ratio including seed number, with the outcome assessor blind and participant blind with allocation concealment:

- 1.) ShamLLLT + ShamIPL
- 2.) LLLT + ShamIPL
- 3.) IPL + ShamLLLT
- 4.) LLLT + IPL

***All groups receive mechanical with pharmacological treatment (Warm compression + Lid hygiene + 1% TTO) for 90 days with google form logbook for record compliance and prevent co-interventional treatments.

***All group with participant/investigator/interpreter blind.

Blinding and Allocation Concealment in Research Team:

1st Research Assistant : Allocates patients according to computer-generated random number allocation, ensuring allocation concealment, Evaluated VA , IOP , OSDI score by reads the questionnaire to the participant

2nd Research Assistant (The treatment administrator) : Administers IPL, LLLT, or sham treatments.

3rd Research Assistant : Conducts assessments using Keratograph and Lipiview2.

Main Researcher : Evaluates primary and secondary outcomes using case record forms, remaining blind to the treatment groups.

Intervention Description

Mechanical with pharmacological treatment : Warm compression 15 minutes + Lid hygiene + 1% TTO for 90 days

1%TTO : OCuSOFT Oust Demodex Eyelid Cleanser Foam Bottle 50ml (OCuSOFT, Richmond, TX) is the only commercially available medication in Thailand that contains 1% tea tree oil.

IPL : The Eye-light device (Espansione Marketing S.p.A., Bologna, Italy, waveleggths 1,200-1,500 nm, Delivery system 12cm²) (Thai FDA No 66-2-2-0012685) :

- Protective eye shields
- 5 flashes of light were applied for each eye (3 along the inferior orbital rim, 1 at the lateral canthus, and 1 applied horizontally along the inferior orbital rim)
- Therapeutic energy level (10–16 joules/ cm²) based on the degree of skin pigmentation.

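### The 20% dropout allowance in section 11 multiplies by 1.2 instead of dividing by 0.8, so 22 per arm covers only about 18% dropout (a minor error)

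*Combined protocol and SAP*

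**What the plan says.** The sample-size paragraph of section 11 (Data Analysis and Statistics) opens with the planned size: "Sampling technique and Sample size: N=22 in each arm by". The method is named as "1-Way ANOVA Pairwise, 2-Sided Equality". The result of the formula is given as "n = Sample size (per pair) = 36, Each arm = 18", and the dropout step follows at once: "20% drop out = 21.6 = 22 per arm". Section 9 (Research Methodology) allocates patients to "4 groups in a 1:1:1:1 ratio", so 22 per arm means 88 patients in total.

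The plan does not say whether the 20% is a share of those randomised or an add-on to the number needed. Later in section 11, under the statistical analysis heading, unavailable data are treated as missing and left out of all calculations. No imputation is planned.

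**The concern.** A dropout rate normally applies to the patients enrolled. To finish with n evaluable patients after losing a fraction d, one enrols n / (1 − d). The plan uses n × (1 + d), which always gives a smaller number. On its own figures, then, the planned enrolment does not quite support the evaluable number it was meant to protect. Because missing outcomes are left out of the analysis, each patient lost before the primary assessment lowers the analysed number, and nothing elsewhere in the plan makes this up.

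With a base of 18, little is at stake. The convention matters more if it is carried into a corrected and much larger sample size.

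**Working it through.** **Inputs, all from section 11 except the number of arms (section 9).** Evaluable per arm 18; dropout 20%; planned 22 per arm; 4 arms; difference 3.18 − 1.59 = 1.59; SD 3.56; two-sided α 0.05 over 6 comparisons; power 80%.

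**1. Reproduce the plan's figure.** 18 × (1 + 0.20) = 21.6, rounded up to 22. This matches exactly. Division gives 22.5, so the printed 21.6 shows that multiplication was used.

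**2. Inflate by division.** 18 / (1 − 0.20) = 22.5, rounded up to 23. Check: 23 × 0.80 = 18.4, which is at least 18. In total, 4 × 23 = 92 against 4 × 22 = 88.

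**3. What 22 per arm gives.** Expected completers at 20% dropout: 22 × 0.80 = 17.6, a shortfall of 18 − 17.6 = 0.4 per arm. Dropout that 22 can absorb: 1 − 18/22 = 18.2%. In whole patients, 4 losses leave 18, and 5 losses (22.7%) leave 17.

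**4. How likely an arm is to keep 18.** Assume that each patient drops out independently with probability 0.20.

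| Enrolled per arm | Expected completers | Chance of at least 18 |
|---|---|---|
| 22 | 17.6 | 54% |
| 23 | 18.4 | 69% |

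With 22 enrolled, the single most likely count is the whole-number part of (22 + 1) × 0.8 = 18.4, that is 18.

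**5. Effect on power.** The plan's own power expression uses z = 1.59 / (3.56 × √(2/n)), compared with the critical value 2.638 for α = 0.05/6 two-sided.
- n = 18: z = 1.340, power 9.7%.
- n = 17.6: z = 1.325, power 9.5%.

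The loss is about 0.2 percentage points. Even with no dropout at all, power would be 12.4% at 22 per arm and 13.1% at 23.

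**6. The base of 18.** The printed formula with the printed inputs is n = 2 × (3.56 × (2.638 + 0.842) / 1.59)² = 121.4, so 122. A formula of this form already gives the size of each arm, so nothing in it supports treating n as a pair total and halving it. With the formula kept as printed, 1 to 6 comparisons, one- or two-sided tests and 80% or 90% power were tried; the smallest result was 62 per arm, or 31 if halved. None gives 18.

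**7. The same step on a corrected base.** 122 × 1.2 = 146.4, so 147 per arm, with 147 × 0.8 = 117.6 expected completers. 122 / 0.8 = 152.5, so 153 per arm. The gap grows to 6 per arm, or 24 in total.

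**The case against.** The best defence is that the plan never defines the 20% as a share of those randomised. Read as a 20% add-on, the multiplication is done correctly. That stands to this extent: the fault is the choice of inflation rule, not a slip in multiplying. But a figure labelled as dropout is ordinarily a proportion of those enrolled. A 20% add-on covers only 1 − 1/1.2 = 16.7% dropout before rounding, and 18.2% once 21.6 is rounded up to 22.

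The second defence is that the consequence is negligible, and this stands in full. The shortfall is less than half a patient per arm, and no conclusion of the trial would turn on 0.2 points of power.

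A reader might infer that the trial will finish with fewer than 18 patients per arm. The documents do not support that: 17.6 is an expectation, 18 remains the most likely count, and an arm keeps at least 18 slightly more often than not. Nor would it be right to describe 17.6 as about 17.

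A reader might also suspect that losses will exceed 20%, because section 4.4 says that moderate and poor compliers with lid scrubbing will be excluded. If this is applied after randomisation, it would draw on the same allowance. The documents give no rate for it, so no size can be put on it.

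**Conclusion.** The point holds as a minor inconsistency. At the stated 20% dropout, 22 per arm is expected to yield 17.6 evaluable patients, 0.4 short of the plan's 18; it keeps 18 only up to 18.2% dropout. This rests on reading 20% as a share of those randomised and on missing outcomes being left out of the analysis, as the plan states. The probabilities of keeping 18 also assume independent dropout.

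It would be tempting to conclude that 23 per arm is the correct size, or that the dropout step is why the trial lacks power. Neither follows. The 18 does not come from the printed formula, which gives about 122 per arm. With 18 evaluable, power is about 10% per comparison at the plan's adjusted level, against the 80% claimed. One more patient per arm leaves that essentially unchanged, so the dropout step should be treated as secondary to the base calculation.

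**What to change.** Keep 22 per arm and restate the line in one of two ways: 22 per arm allows for 18% dropout (22 × 0.82 = 18.04), or about 17.6 evaluable patients per arm are expected at 20% dropout. Either is a one-line edit to section 11 with no change to recruitment.

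When the base sample size and power are re-derived, define dropout as a proportion of those randomised and inflate by n / (1 − dropout). Making both changes in the same revision adds almost no work. Changing 22 to 23 alone is not recommended, since it would add four patients in total and still rest on a base of 18 that the formula does not give.

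### One difference of 1.59 is used to claim 80% power for all six pairs, which does not fit the hypotheses for LLLT versus IPL or for the combination versus each single light

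*Combined protocol and SAP*

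**What the plan says.** Section 11 (Sampling technique and Sample size) uses the method "1-Way ANOVA Pairwise, 2-Sided Equality" with a 5% significance level, 80% power, SD 3.56, means 3.18 and 1.59, and "τ = the number of comparisons to be made = 6". The basis of the difference is given as "Relative difference (δ) = 50% (or 0.50) by our expert opinion of minimal clinical significant difference". Neither mean is assigned to an arm, and no third or fourth mean, equivalence margin or interaction effect is stated. The result is 36 per pair, 18 per arm, and 22 per arm after a 20% allowance for dropout.

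Section 6 (Hypothesis) makes three kinds of statement about the same four arms:

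- The alternative hypothesis is that at least one light therapy gives a reduction "greater than Mechanical with pharmacological Treatment".
- The two single lights are expected to be equal: "LLLT or IPL, will be equally effective in reducing Demodex mite count".
- The combination is expected to be superior: "IPL + LLLT will be more effective than LLLT or IPL alone in reducing Demodex mite count". No size is attached.

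**The concern.** A single pairwise difference serves contrasts that the plan itself expects to behave differently: three comparisons with control, one pair expected to be equal, and two pairs in which the comparator may already have had most of the available reduction. If the 80% figure is read as applying to all six, two misreadings become likely. A non-significant LLLT versus IPL result could be reported as confirming equal efficacy. A non-significant combination result could be reported as no added benefit. The second matters because joint action of the two lights is the subject of the plan's first novel question.

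**Working it through.** **Inputs (all from section 11).** σ = 3.56; α = 0.05 two-sided; τ = 6; power 80% (z = 0.8416); μA − μB = 1.59. Critical values z(1 − α/(2τ)) are 2.638 for τ = 6, 2.394 for τ = 3 and 1.960 unadjusted. Unadjusted figures are shown as well because the statistical analysis text sets p < 0.05 and names no pairwise adjustment.

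**Step 1: the plan's own figure.** n = 2 × [3.56 × (2.638 + 0.8416) / 1.59]² = 121.4, so 122. This is n per arm: the plan's power formula uses σ√(2/n), the standard error of a difference between two means with n in each. The plan's 18 does not reproduce. Taking τ from 1 to 6, one- or two-sided, with 80% or 90% power, and halving n or not, never gives 18 or 36 at these means and SD.

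**Step 2: which differences fit section 6.**

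- *LLLT versus IPL.* The hypothesised difference is 0, not 1.59. At a true difference of 0 the test rejects at its alpha whatever n is: 0.05/6 = 0.83% at τ = 6, 5% unadjusted.
- *Combination versus each single light.* Suppose each light alone reaches the plan's 50% reduction, a mean of 1.59. A further 1.59 takes the combination to 1.59 − 1.59 = 0. A count cannot be negative, so a mean of 0 means no mites in any patient, and then the SD is 0, not 3.56. The plan's 50% rule applied to 1.59 gives 0.5 × 1.59 = 0.795.

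**Step 3: sample size and power from the plan's formulas, SD 3.56.** Power is Φ(z − z_crit) + Φ(−z − z_crit), with z = difference / (3.56 √(2/n)).

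| True difference | Adjustment | n per arm for 80% | Power, 18 per arm | Power, 22 per arm |
|---|---|---|---|---|
| 1.59 | τ = 6 | 122 | 9.7% | 12.4% |
| 1.59 | τ = 3 | 105 | 14.6% | 18.1% |
| 1.59 | none | 79 | 26.8% | 31.6% |
| 0.795 | τ = 6 | 486 | 2.5% | 2.9% |
| 0.795 | none | 315 | 10.3% | 11.5% |

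Example: at 0.795 and 18 per arm, z = 0.795 / (3.56 × √(2/18)) = 0.670. Then Φ(0.670 − 2.638) + Φ(−0.670 − 2.638) = 0.0245 + 0.0005 = 2.5%.

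**Step 4: sensitivity to the SD.** The value 3.56 is a baseline SD, and the SD of a count may fall as its mean falls. Assume SD/mean stays at 3.56/3.18. The SDs are then 1.78 at mean 1.59 and 0.89 at mean 0.795, and the summed variance is 3.168 + 0.792 = 3.960. The requirement is n = 3.960 × (2.638 + 0.8416)² / 0.795² = 75.9, so 76 per arm at τ = 6, and 50 unadjusted. With 18 per arm, power is about 17% and 40%.

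**Step 5: what a null LLLT versus IPL result could show.** With SD 3.56 the 95% CI half-width is 1.96 × 3.56 × √(2/18) = 2.33 at 18 per arm, and 1.96 × 3.56 × √(2/22) = 2.10 at 22. An interval centred on zero would still contain a difference of 1.59 in either direction, which is the plan's own minimal important difference.

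**The case against.** Several arguments on the other side have force.

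*The 1.59 is a minimal important difference.* Sizing each pair at such a value does not assert that every pair truly differs by it. That stands: the combination pairs are formally among the six sized, so it would be wrong to say they were not sized. It does not rescue the power claim, because the standard is a relative 50%, and against a single-light mean of 1.59 that is 0.795.

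*A reader might infer that the hypotheses make 1.59 impossible for three of the six pairs.* The documents do not support that. Control, LLLT and IPL all at 3.18 with the combination at 1.59 satisfies every statement in section 6 and gives exactly 1.59 against each single light. The first novel question contemplates synergy, so this is not fanciful. Only LLLT versus IPL is contradicted outright. The other two pairs lose 1.59 only if each single light already reaches 1.59. The counterexample has its own price: both single lights must then add nothing over sham.

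*A reader might also infer that τ = 6 is wasteful and should be 3.* The null hypothesis and primary objective compare all four treatments, and section 6 adds comparisons among the light arms. Six is defensible.

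*The larger error is 122 versus 18 per arm.* That is correct. It affects every pair, and the two corrections belong together.

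*The figure of 486 depends on holding the SD at 3.56.* Also correct. The range down to 50–76 per arm must be shown, but even its lower end is more than double 22.

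**Conclusion.** The point holds in this form: the 80% power statement cannot stand for LLLT versus IPL or for the combination versus each single light. For the first pair, the test does not address the hypothesis and no margin is given, so non-significance must not be read as equivalence. For the other two, no effect size is stated. The shortfall at a further halving rests on two assumptions: that each single light reaches 1.59, and either a constant SD of 3.56 or an SD proportional to the mean. Under both SD assumptions the planned 18–22 per arm is well below the requirement. The conclusion about power does not depend on the first assumption, because at a true difference of 1.59 the plan's own formula still gives only about 10–12% at τ = 6.

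**What to change.** In section 11:

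- Withdraw the 80% power statement for these three pairs. Correct the base calculation (122 per arm from the stated inputs at τ = 6), and state the actual power at 18–22 per arm for each contrast.
- State the difference assumed for the combination versus a single light, and the SD assumption behind it.
- Report LLLT versus IPL and the combination versus each single light as estimates with 95% CIs. Say in advance that a non-significant result supports neither equivalence nor a conclusion of no added benefit.
- Keep τ equal to the number of comparisons actually tested: 6 if all pairs are tested. Reducing it to the three comparisons with control is optional and does not restore 80% power, since 105 per arm would be needed and 18–22 gives 14.6–18.1% at 1.59.

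The cost is protocol and SAP wording, with no extra patients. The downside is that the stated power becomes less favourable.
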